#### **10.5.3.3 Laboratory abnormalities**

For laboratory tests covered by the CTCAE version 4.03, the study's biostatistical and reporting team will grade laboratory data accordingly. For laboratory tests covered by CTCAE, a grade 0 will be assigned for all non-missing values not graded as 1 or higher. Further details will be specified in the reporting analysis plan (RAP). Grade 5 will not be used.

For laboratory tests where grades are not defined by CTCAE, results will be graded by the low/normal/high classifications based on laboratory normal ranges.

The following summaries will be generated separately for hematology, biochemistry and urinary laboratory tests by cohort/sub-cohort:

- shift tables using CTCAE grades to compare baseline to the worst on-treatment value
- for laboratory tests where CTCAE grades are not defined, shift tables using the low/normal/high/(low and high)

Listing of all laboratory data with values flagged to show the corresponding CTCAE grades and the classifications relative to the laboratory normal ranges will be generated.

A separate listing will display notable laboratory abnormalities (i.e., newly occurring CTCAE grade 3 or 4 laboratory toxicities).

In addition to the above mentioned tables and listings, other exploratory analyses, for example figures plotting time course of raw or change in laboratory tests over time or box plots might be specified in the RAP.

#### **10.5.3.4 Other safety data**

Data from other tests (including ECGs and vital signs) will be summarized and listed by cohort/sub-cohort. Notable values will be flagged, and any other information collected will be listed as appropriate. Definitions of notably abnormal results will be provided in the RAP.

#### **10.5.3.5 Tolerability**

Tolerability will be summarized in terms of dose reductions or drug interruption due to an AE by cohort/sub-cohort.

### **10.5.4 Pharmacokinetics**

[figure not shown]
The PAS will be used in all pharmacokinetic data analysis and PK summary statistics. Summary statistics of plasma concentration of INC280 and its relevant metabolites will be reported by visit for all patients that provided at least one evaluable PK sample. Summary statistics include n, arithmetic mean, median, SD, geometric mean, coefficient of variation (CV) (%) and geometric CV (%), minimum and maximum. PK parameters as listed in [Table 10-1](#) will be derived using non-compartmental analysis with the aid of WinNonlin Pro (Version 5.0 or higher) and reported, if feasible. Graphical presentation will be provided on mean concentration at each scheduled time point for PK sub-population where the full PK profile is available. In addition, summary statistics on PK parameters will be reported for PAS.

[figure not shown]
Concentration values below the lower limit of quantitation (LLOQ) will be displayed in listings as zero with a flag and handled as zero in any calculations of summary statistics, but handled as missing for the calculation of the geometric means and their CV. Any missing PK parameter data will not to be imputed.

**Table 10-1 Noncompartmental pharmacokinetic parameters**

AUC inf	The AUC from time zero to infinity (mass x time x volume-1)
AUC 0-t	The AUC from time zero to defined time t (mass x time x volume-1)

[figure not shown]
AUCtau	The AUC within the dosing interval ( $\tau$ ) (mass x time x volume-1)
Cmax	The maximum (peak) observed plasma, blood, serum, or other body fluid drug concentration after single dose administration (mass x volume-1)
Tmax	The time to reach maximum (peak) plasma, blood, serum, or other body fluid drug concentration after single dose administration (time)
T1/2	The elimination half-life associated with the terminal slope ( $\lambda_z$ ) of a semi logarithmic concentration-time curve (time). Use qualifier for other half-lives
CL/F	The apparent total body clearance of drug from the plasma (volume x time-1)
Vz/F	The apparent volume of distribution during terminal phase (associated with $\lambda_z$ ) (volume)
Racc	Accumulation ratio

#### 10.5.6 Resource utilization

Not applicable.

#### 10.7 Interim analysis

In Cohort 1, the interim analysis will be performed separately for each of the two sub-cohorts. Interim analyses for each cohort/sub-cohort are planned when at least 28 patients in each of Sub-cohorts 1a and 1b, Cohorts 2 and 4, and 20 patients in Cohort 3 have completed at least 6 cycles of treatment (18 weeks) or have discontinued treatment earlier. For the interim analysis and the final analysis in Cohort 2 (cMET GCN  $\geq 4$  and  $< 6$ ), the study targets to have at least 40% of patients with cMET GCN  $\geq 5$  and  $< 6$ .

No interim analysis for futility is planned for Sub-cohorts 5a and 5b, Cohort 6 and Cohort 7.

The decision to stop for futility for the respective cohort/sub-cohort at interim will be based on the probability of success (POS). POS is the probability of a positive conclusion of the

study if the study continued beyond interim, (i.e., till the final analysis), given the interim observed data (x) and success among n patients. Thus,

$$POS = \text{Prob}[\text{ Final observed ORR} \geq 35\% \mid x, n]$$

Minimally informative Beta distribution prior ([Neuenschwander et al 2008](#)) with prior mean equal to 25% will be used, i.e., the prior distribution will be Beta (0.3333, 1) for the POS calculations at the interim analysis.

The respective cohort will be stopped for futility at the interim analysis if the respective POS < 10%. The interim analysis will be performed by cohort in which the patients are enrolled. In addition, for Sub-cohort 1a and 1b, Cohorts 2 and 3, sensitivity analysis on the primary endpoint may be performed at interim analysis excluding patients with cMET mutations.

All evaluable patients at the time of the data cut-off for the interim analysis will be used to obtain the futility boundary using the POS criteria. The futility boundary will be calculated according to the actual number of evaluable patients in the interim analysis.

#### **Sub-cohort 1a, Sub-cohort 1b, Cohort 2 and Cohort 4**

With 28 evaluable patients for interim analysis in each of the Sub-cohorts 1a and 1b, Cohorts 2 and 4, if  $\leq 7$  responses (POS = 0.0543) are observed then the respective cohort/sub-cohort will be stopped for futility. Further details of POS are provided in With 28 evaluable patients for interim analysis in each of the Sub-cohorts 1a and 1b, Cohorts 2 and 4, if  $\leq 7$  responses (POS = 0.0543) are observed then the respective cohort/sub-cohort will be stopped for futility. Further details of POS are provided in [Table 10-2](#). For each of the Sub-cohorts 1a and 1b, Cohorts 2 and 4, if at the time that the 28th patient is enrolled a minimum of 8 responders have not yet been observed, accrual in the cohort/sub-cohort may be temporarily suspended until either the minimum number of 8 responders are observed or results of the interim analysis allow that cohort/sub-cohort to continue.

**Table 10-2 Probability of Success at the Final Analysis Based on Various Number of Responders Observed at IA for Sub-cohort 1a, Sub-cohort 1b, Cohort 2 and Cohort 4**

Responder at IA out of 28 evaluable patients at IA	Probability of Success
$\leq 5$	< 0.01
6	0.0164
7	0.0543
8	0.1398
9	0.2863
10	0.4794
11	0.6766
$\geq 12$	> 0.83

**Table 10-3 Number of Responders for Various Number of Evaluable Patients at Interim Analyses by Required Probability of Success for Sub-cohort 1a, Sub-cohort 1b, Cohort 2 and Cohort 4**

Number of Evaluable patients at IA	Responders at IA	Probability of Success
26	6	0.0368
26	7	0.1050

Number of Evaluable patients at IA	Responders at IA	Probability of Success
27	7	0.0765
27	8	0.1829
28	7	0.0543
28	8	0.1398
29	7	0.0377
29	8	0.1044
30	8	0.0760
30	9	0.1792
31	8	0.0540
31	9	0.1369
32	8	0.0373
32	9	0.1020
33	9	0.0740
33	10	0.1739
34	9	0.0523
34	10	0.1323
35	10	0.0980
35	11	0.2152

### Cohort 3

With 20 evaluable patients for interim analysis in Cohort 3 if  $\leq 5$  responses (POS=0.0999) are observed then the cohort will be stopped for futility. All evaluable patients at the time of the data cut-off for the interim analysis will be used to obtain the futility boundary using the POS criteria. Further details of POS are provided in [Table 10-4](#). If at the time that the 20th patient is enrolled a minimum of 6 responders have not yet been observed, accrual in the cohort may be temporarily suspended until either the minimum number of 6 responders are observed or results of the interim analysis allow the cohort to continue.

**Table 10-4 Probability of Success at the Final Analysis Based on Various Number of Responders Observed at IA for Cohort 3**

Responder at IA out of 20 evaluable patients at IA	Probability of Success
1	0.0001
2	0.0009
3	0.0066
4	0.0309
5	0.0999
6	0.2379
7	0.4382
8	0.6533

### 10.8 Sample size calculation

Approximately 456 patients (69 patients per Sub-cohort in Cohort 1 and 69 patients per cohort in Cohorts 2-4, 27 patients per each Sub-cohort in Cohort 5, approximately 30 patients in Cohort 6 and approximately 27 in Cohort 7) will be enrolled in the study if none of the four cohorts (Cohort 1-4) is stopped for futility at the time of the interim analysis. The exact 95% CIs for various sample sizes and observed ORRs in each cohort/sub-cohort are shown in

**Table 10-5** for Sub-cohorts 1a and 1b and Cohorts 2, 3 and 4, and in **Table 10-6** for Sub-cohorts 5a, 5b and Cohort 7.

**Table 10-5      Exact Binomial 95 percent Confidence Intervals for Various Sample Sizes and Observed ORRs in each Cohort/Sub-cohort 1a, 1b, 2, 3 and 4**

Sample size (N)	Number of responders	Observed ORR (%)	95% exact CI (%)
65	23	35.4	23.9
66	24	36.4	24.9
67	24	35.8	24.5
68	24	35.3	24.1
69	25	36.2	25.0
70	25	35.7	24.6
71	25	35.2	24.2
72	26	36.1	25.1
			48.3

**Table 10-6      Exact Binomial 95 percent Confidence Intervals for Various Sample Sizes and Observed ORRs in each Sub-cohort 5a, 5b and Cohort 7**

Sample size (N)	Number of responders	Observed ORR (%)	95% exact CI (%)
25	14	56.0	34.9
26	15	57.7	36.9
27	15	55.6	35.3
28	16	57.1	37.2
29	16	55.2	35.7
			73.6

The operating characteristics (with 69 subjects per cohort/Sub-cohort 1a, 1b, 2, 3 and 4) are shown in **Table 10-7** and **Table 10-8**. The tables show probability of stopping at interim, probability for positive conclusion (i.e., not stopped at IA for futility and success criteria met at final analysis) and negative conclusion (i.e., not stopped at IA for futility but success criteria not met at final analysis) under different underlying true ORR. The operating characteristics (with 27 subjects per Sub-cohort in 5a, 5b and Cohort 7) are shown in **Table 10-9**. The table shows the probability of meeting the success criteria under different underlying true ORR.

#### **Sub-cohort 1a, Sub-cohort 1b, Cohort 2 and Cohort 4**

The operating characteristics at this sample size have > 50% probability of stopping the trial for futility when the true ORR is < 25%. Also, when the true ORR is 35% then the probability of positive conclusion at the final analysis with 69 patients is  $\geq 44\%$ . If the true ORR is 45% or higher, the probability of positive conclusion at the final analysis with 69 patients is > 90%.

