### 10.4.2 Statistical hypothesis, model, and method of analysis

The primary analysis will be performed on the FAS. The primary efficacy endpoint ORR will be estimated and the exact 95% confidence interval (CI) ([Clopper and Pearson 1934](#)) provided by cohort/sub-cohort.

In Cohorts 1-4, treatment with INC280 would be considered to have clinically relevant efficacy in a cohort/sub-cohort if an ORR of ~35% is observed in that cohort for the corresponding primary analysis.

In addition, 5 hypotheses will be tested as following for the cohorts/sub-cohorts respectively ( $H_{i0}$  and  $H_{i1}$  correspond to cohort/sub-cohort i where  $i=1a, 1b, 2, 3$  or  $4$ )

$H_{i0}$ : ORR  $\leq 25\%$

In favor of the alternative

$H_{i1}$ : ORR  $> 25\%$

For Sub-cohorts 5a, 5b and Cohort 7, treatment with INC280 would be considered to have clinically relevant efficacy if an ORR of ~55% is observed in that cohort for the corresponding primary analysis. In addition, 3 hypotheses will be tested as following for the cohorts/sub-cohorts ( $H_{i0}$  and  $H_{i1}$  correspond to Sub-cohort i where  $i=5a, 5b$  or  $7$ ):

$H_{i0}$ : ORR  $\leq 35\%$

In favor of the alternative

$H_{i1}$ : ORR  $> 35\%$

The tests will be performed based on the exact CI for ORR in each cohort/sub-cohort using a one-sided  $\alpha=0.025$  level. Based on historical data, as referred in [Section 1.1.1](#), a 25% ORR is a reasonable threshold to be considered as clinically relevant in this specific setting of second and third line advanced NSCLC patients ([de Marinis 2008](#), [Weiss 2013](#), [NCCN Guidelines 2014](#)) in Cohorts/Sub-cohorts 1a, 1b, 2, 3 and 4. Similarly, a 35% ORR is a reasonable threshold to be considered as clinically relevant in the treatment-naïve setting for advanced NSCLC patients ([Zhou 2015](#), [Scagliotti 2008](#)) in Sub-cohorts 5a, 5b and Cohort 7. Since a one sided  $\alpha=0.025$  is used for a particular hypothesis testing, the testing will be conducted based on two-sided 95% exact confidence interval. The null hypothesis will be rejected if the lower bound of the two-sided 95% exact CI is  $>25\%$  in Cohorts/Sub-cohorts 1a, 1b, 2, 3 and 4. And

the null hypothesis will be rejected in Sub-cohorts 5a and 5b if the lower bound of the two-sided 95% exact CI is >35%.

No hypothesis testing is planned for Cohort 6.

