2.7.2 Statistical hypothesis, model, and method of analysis

The primary analysis will be performed on the FAS. The primary efficacy endpoint ORR will be estimated and the exact 95% confidence interval (CI) ([Clopper and Pearson 1934](#)) provided by cohort.

Treatment with INC280 will be considered to have clinically relevant efficacy in cohort (1-4) if an ORR of $\sim 35\%$ is observed in that cohort with lower bound of exact 95% CI greater than 25%. Whereas, in cohorts (5a and 5b and 7), treatment with INC280 will be considered to have clinically relevant efficacy if an ORR of $\sim 55\%$ is observed in that cohort with lower bound of exact 95% CI greater than 35%.

No hypothesis testing is planned for cohort 6.

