2.9 Sample size calculation

Approximately 456 patients (69 patients per cohort in Cohorts 1a, 1b, 2, 3, 4 and 27 patients per each Cohort 5a, 5b, approximately 30 patients in Cohort 6 and approximately 27 patients in Cohort 7) will be enrolled in the study if none of the cohorts 1-4 is stopped for futility at the time of the interim analysis. The exact 95% CIs for various sample sizes and observed ORRs in each cohort 1-4 are shown in [Table 2-4](#) and in [Table 2-5](#) for cohorts 5a, 5b and 7.

Table 2-4 **Exact Binomial 95 percent Confidence Intervals for Various Sample Sizes and Observed ORRs in Each Cohort**

Sample size (N)	Number of responders	Observed ORR (%)	95% exact CI (%)
65	23	35.4	23.9
66	24	36.4	24.9
67	24	35.8	24.5
68	24	35.3	24.1
69	25	36.2	25.0
70	25	35.7	24.6
71	25	35.2	24.2
72	26	36.1	25.1

Table 2-5 **Exact Binomial 95 percent Confidence Intervals for Various Sample Sizes and Observed ORRs in each cohort 5a, 5b and 7**

Sample size (N)	Number of responders	Observed ORR (%)	95% exact CI (%)
25	14	56.0	34.9
26	15	58.0	36.9
27	15	55.6	35.3
28	16	57.1	37.2
29	16	55.2	35.7

The operating characteristics (with 69 patients per cohort in 1a, 1b, 2, 3 and 4) are shown in [Table 2-6](#) and [Table 2-7](#). The tables show probability of stopping at interim, probability for positive conclusion (i.e., not stopped at IA for futility and success criteria met at final analysis) and negative conclusion (i.e., not stopped at IA for futility but success criteria not met at final analysis) under different underlying true ORR. The operating characteristics (with 27 patients per cohort in 5a, 5b and 7) are shown in [Table 2-8](#). The table shows the probability of meeting the success criteria under different underlying true ORR.

Cohort 1a, Cohort 1b, Cohort 2 and Cohort 4

The operating characteristics at this sample size have $> 50\%$ probability of stopping the trial for futility when the true ORR is $< 25\%$. Also, when the true ORR is 35% then the probability of positive conclusion at the final analysis with 69 patients is $\geq 44\%$. If the true ORR is 45% or higher, the probability of positive conclusion at the final analysis with 69 patients is $> 90\%$.

Table 2-6 Operating Characteristics for Cohort 1 (MET GCN ≥ 6) and Cohort 2 (MET GCN ≥ 4 and < 6)

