2.11 Interim analysis for futility

In Cohort 1, the interim analysis for futility will be performed separately for each of the two cohorts. Interim analyses for futility for each cohort are planned when at least 28 patients in each of Cohorts 1a, 1b, 2 and 4, and 20 patients in Cohort 3 have completed at least 6 cycles of treatment (18 weeks) or have discontinued treatment earlier. Due to the expected difference in enrollment rate for each cohort, the interim analysis for the different cohorts may occur at different times. For the interim analysis and the final analysis in Cohort 2 (MET GCN ≥ 4 and

< 6), the study targets to have at least 40% of patients with MET GCN ≥ 5 and < 6. No interim analysis is planned for Cohorts 5a, 5b and 6.

The decision to stop for futility for the respective cohort at interim will be based on the probability of success (POS). POS is the probability of a positive conclusion of the study if the study continued beyond interim, (i.e., till the final analysis), given the interim observed data (x) and success among n patients. Thus,

$$\text{POS} = \text{Prob}[\text{Final observed ORR} \geq 35\% \mid x, n]$$

Minimally informative Beta distribution prior ([Neuenschwander 2008](#)) with prior mean equal to 25% will be used, i.e., the prior distribution will be Beta (0.3333, 1) for the POS calculations at the interim analysis.

The respective cohort will be stopped for futility at the interim analysis if the respective POS < 10%.

Cohort 1a, Cohort 1b, Cohort 2 and Cohort 4

With 28 evaluable patients for interim analysis in each of the Cohorts 1a, 1b, 2 and 4, if ≤ 7 responses (POS = 0.0543) are observed then the respective cohort will be stopped for futility. Further details of POS are provided in [Table 2-9](#). For each of the Cohorts 1a, 1b, 2 and 4, if at the time that the 28th patient is enrolled a minimum of 8 responders have not yet been observed, accrual in the cohort may be temporarily suspended until either the minimum number of 8 responders are observed or results of the interim analysis allow that cohort to continue.

Table 2-9 Probability of Success at the Final Analysis Based on Various Number of Responders Observed at IA for Cohort 1a, Cohort 1b, Cohort 2 and Cohort 4

Responder at IA out of 28 evaluable patients at IA	Probability of Success
≤ 5	< 0.01
6	0.0164
7	0.0543
8	0.1398
9	0.2863
10	0.4794
11	0.6766
≥ 12	> 0.83

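### At 69 patients the >25% lower-bound rule needs 26 responders, not 25, so the stated 44% probability of success at a true ORR of 35% is 35%

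*Protocol*

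**What the plan says.** Each of Sub-cohorts 1a and 1b and Cohorts 2, 3 and 4 is sized at 69 patients (Protocol 10.8: "69 patients per Sub-cohort in Cohort 1 and 69 patients per cohort in Cohorts 2-4").

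**Final rule.** Protocol 10.4.2 tests ORR ≤ 25% at one-sided α = 0.025, and "the testing will be conducted based on two-sided 95% exact confidence interval". The null is rejected only if the lower bound is strictly above 25%. SAP 2.7.2 requires an observed ORR of about 35% that "is observed in that cohort with lower bound of exact 95% CI greater than 25"%.

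**Planned row.** Protocol Table 10-5 and SAP Table 2-4 give, for the planned size, N, responders, ORR and lower bound as "69 25 36.2 25.0".

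**Operating characteristics.** Protocol 10.8 and SAP 2.9 define a positive conclusion as passing the interim and meeting the success criteria at the final analysis. Protocol Table 10-7 (SAP Table 2-6) gives 44.00% at a true ORR of 35%, and the text repeats it: "when the true ORR is 35% then the probability of positive conclusion at the final analysis with 69 patients is" at least 44%. Protocol Table 10-8 (SAP Table 2-7) gives 41.41% for Cohort 3.

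**Interim rule.** In SAP 2.11, as in Protocol 10.7, "POS is the probability of a positive conclusion of the study if the study continued beyond interim". The formula that follows is the probability that the final observed ORR is at least 35%. A cohort stops if POS is below 10%.

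**The concern.** The lower bound in the planned row is printed as exactly the value that must be exceeded. If the unrounded bound is at or below 25%, the count of 25 responders shown there is not a success, and any operating characteristic that treats it as one is too favourable. The 35% scenario matters most, because that is the response rate the plan itself calls clinically relevant.

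Three things follow:

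- The stated success probabilities are wrong for five of the eight hypothesis tests.
- A cohort finishing at 25/69 would count as a success in the operating-characteristics tables and as a failure under Protocol 10.4.2.
- The futility POS is called the probability of a positive conclusion but is computed for an easier target than the final test.

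The SAP says that its Section 2 will be imported into the clinical study report, so the figures would carry over.

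**Working it through.** **Inputs.** N = 69; null ORR 25%; one-sided α 0.025 through the two-sided 95% Clopper-Pearson interval (Protocol 10.4.2, 10.8). Interim at 28 evaluable patients, stop at ≤ 7 responders; for Cohort 3, 20 patients and ≤ 5 (Protocol 10.7). POS prior Beta(1/3, 1).

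**1. How many responders are needed?** The lower bound for x of n is the 2.5% quantile of Beta(x, n − x + 1). It exceeds 25% exactly when P(X ≥ x | n, 0.25) < 0.025.

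| Responders of 69 | ORR | Lower bound | P(X ≥ x, p = 0.25) | Bound > 25%? |
|---|---|---|---|---|
| 25 | 36.2% | 24.9949% | 0.02506 | No |
| 26 | 37.7% | 26.29% | 0.01333 | Yes |

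The exact one-sided p-value that SAP 4.6.4 asks for gives the same answer: 0.02506 is above 0.025.

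**2. Reproduce the plan's tables.** With R responders required at the end,

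P(positive) = Σ over k = 8…28 of Bin(k; 28, p) × P(Bin(41, p) ≥ R − k).

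For Cohort 3, k runs from 6 to 20 and the second stage has 49 patients. With R = 25 every row of Protocol Tables 10-7 and 10-8 is reproduced to the printed decimals. At p = 0.35 with the 28-patient interim, R = 24 gives 52.79%, R = 25 gives 44.00% and R = 26 gives 35.13%. The tables therefore count 25/69 as success.

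**3. Apply the written rule (R = 26, same futility boundaries).**

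| True ORR | 1a, 1b, 2, 4: stated | At ≥ 26 | Cohort 3: stated | At ≥ 26 |
|---|---|---|---|---|
| 25% | 2.34% | 1.27% | 2.17% | 1.19% |
| 30% | 15.01% | 10.11% | 13.98% | 9.50% |
| 35% | 44.00% | 35.13% | 41.41% | 33.31% |
| 40% | 75.38% | 68.00% | 71.99% | 65.25% |
| 45% | 93.11% | 90.06% | 90.46% | 87.68% |
| 50% | 98.73% | 98.09% | 97.36% | 96.77% |

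The largest gap is at 35%: 44.00 − 35.13 = 8.87 percentage points.

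**4. Interim POS.** An observed ORR of at least 35% of 69 means at least 25 responders (24/69 = 34.8%, 25/69 = 36.2%). Given x of n, the remaining responders follow a beta-binomial with parameters 1/3 + x and 1 + n − x over 69 − n patients.

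- At 7/28, POS is 0.0543 for ≥ 25, as printed, and 0.0358 for ≥ 26.
- At 8/28, POS is 0.1398 for ≥ 25, as printed, and 0.0999 for ≥ 26, just under the 10% limit.
- If POS were tied to ≥ 26, the stopping boundary would rise by one responder at 26, 28, 29, 31, 32 and 34 evaluable patients. It would not move at 27, 30, 33 or 35.
- Cohort 3's boundary stays at ≤ 5/20 (6/20 gives 0.1919).
- Moving the 28-patient boundary to ≤ 8 would lower the 35.13% further, to 33.21%.

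**The case against.** The strongest reply is that the tables are correct for a different criterion. POS is written as the probability of a final observed ORR of at least 35%, and Protocol 10.4.2 introduces the hypothesis tests as an addition to the clinical-relevance threshold of about 35%. If a positive conclusion means only that point estimate, 25/69 qualifies and 44.00% is right. That explains where the number came from, but it does not rescue it. Protocol 10.8 says the success criteria must be met, SAP 2.7.2 joins the ORR and the lower bound in one condition, and Protocol Table 10-9, for Sub-cohorts 5a and 5b and Cohort 7, applies both. There the boundary case does pass: 15/27 has a lower bound of 35.33%.

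Several limits on the consequences do stand:

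- Table 10-5 is rounded correctly and has no pass/fail column.
- Type I error is controlled. The final test as written fails 25/69, and even a ≥ 25 rule with the 28-patient interim gives 2.34% at a true ORR of 25%.
- The more-than-90% statement at a true ORR of 45% survives narrowly for 1a, 1b, 2 and 4 (90.06%). The text statements about the probability of stopping are unaffected.
- Sub-cohort 1b and Cohorts 2 and 3 closed for futility with 42, 54 and 30 patients enrolled, so the 69-patient threshold never applied to them. Cohort 4's preliminary result (39.1%, CI 27.6–51.6, n = 69) clears the bound either way.
- The interims are finished, so redefining POS now could change no decision. The 8/28 example is also very close: 9.992% against 10%.

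**Conclusion.** The concern holds. Under the rule in both documents, success at 69 patients needs 26 responders (37.7%). At a true ORR of 35% the probability of a positive conclusion is 35.13% rather than 44.00%, and in Cohort 3 it is 33.31% rather than 41.41%. The error lies in the stated success probabilities and in the target used for POS, not in the false-positive rate of the final test.

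These figures assume exactly 69 patients in the analysis, interims at exactly 28 or 20 evaluable patients, the stated futility boundaries, and a strict reading of the 25% limit. Rounding the bound to 25.0 does not help, since 25.0 is not above 25. Closed cohorts and Cohort 4's margin limit the practical effect, but the printed probabilities are still wrong.

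**What to change.** 1. In Protocol 10.8 and SAP 2.9, state that success at N = 69 requires at least 26 responders (37.7%; lower bound 26.29%).
2. In Protocol Table 10-5 and SAP Table 2-4, show the lower bound for 25/69 as 24.99% and mark it as not meeting the criterion.
3. Recompute the positive- and negative-conclusion columns of Protocol Tables 10-7 and 10-8 and SAP Tables 2-6 and 2-7 at ≥ 26. Replace at least 44% with at least 35% in the protocol summary, Protocol 10.8 and SAP 2.9.
4. In Protocol 10.7 and SAP 2.11, state that POS uses an observed ORR of at least 35% (at least 25/69), which is looser than the final success rule. Since the interims have been run, this is preferable to redefining POS.

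The cost is wording and table changes in the two documents, with no extra patients. The stated success probabilities become less favourable by up to about 9 percentage points.
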